7.6.2. Instructions for Reporting Special Situations

7.6.2.1. Instructions for Reporting Pregnancies

The investigator should report pregnancies in female study subjects that are identified after initiation of study medication and throughout the study, including the post study drug follow-up period, to Gilead DSPH using the pregnancy report form within 24 hours of becoming aware of the pregnancy.

Refer to eCRF completion guidelines for full instructions on the mechanism of pregnancy reporting.

The pregnancy itself is not considered an AE nor is an induced elective abortion to terminate a pregnancy without medical reasons.

Any premature termination of pregnancy (e.g., a spontaneous abortion, an induced therapeutic abortion due to complications or other medical reasons) must be reported within 24 hours as an SAE. The underlying medical reason for this procedure should be recorded as the AE term.

A spontaneous abortion is always considered to be an SAE and will be reported as described in Section 7.1.2 Furthermore, any SAE occurring as an adverse pregnancy outcome post study must be reported to Gilead DSPH.

The subject should receive appropriate monitoring and care until the conclusion of the pregnancy. The outcome should be reported to Gilead DSPH using the pregnancy outcome report form. If the end of the pregnancy occurs after the study has been completed, the outcome should

be reported directly to Gilead DSPH. Gilead DSPH contact information is as follows: Email: **PPD** and Fax: **PPD**

Refer to [Appendix 5](#) for Pregnancy Precautions, Definition for Female of Childbearing Potential, and Contraceptive Requirements.

7.6.2.2. Reporting Other Special Situations

All other special situation reports must be reported on the special situations report form and forwarded to Gilead DSPH within 24 hours of the investigator becoming aware of the situation. These reports must consist of situations that involve study IMP and/or Gilead concomitant medications, but do not apply to non-Gilead concomitant medications.

Special situations involving non-Gilead concomitant medications does not need to be reported on the special situations report form; however, for special situations that result in AEs due to a non-Gilead concomitant medication, the AE should be reported on the AE form.

Any inappropriate use of concomitant medications prohibited by this protocol should not be reported as “misuse,” but may be more appropriately documented as a protocol deviation.

Refer to eCRF completion guidelines for full instructions on the mechanism of special situations reporting.

All clinical sequelae in relation to these special situation reports will be reported as AEs or SAEs at the same time using the AE eCRF and/or the SAE report form. Details of the symptoms and signs, clinical management, and outcome will be reported, when available.

8. STATISTICAL CONSIDERATIONS

8.1. Analysis Objectives and Endpoints

8.1.1. Analysis Objectives

The primary objective:

Phase 1b Dose Escalation

- To characterize the safety and tolerability of GS-5829 in combination with fulvestrant and exemestane in subjects with advanced ER+/HER2- BrCa
- To determine the MTD or RP2D of GS-5829 in combination with fulvestrant in subjects with advanced ER+/HER2- BrCa

Randomized Phase 2 Dose Expansion

- To evaluate the efficacy of GS-5829 in combination with fulvestrant compared to fulvestrant alone in subjects with advanced ER+/HER2- BrCa, as measured by PFS

Secondary objectives:

Phase 1b Dose Escalation

- To evaluate the pharmacokinetics of GS-5829 in combination with fulvestrant in subjects with advanced ER+/HER2- BrCa

Randomized Phase 2 Dose Expansion

- To evaluate the efficacy of GS-5829 in combination with fulvestrant compared to fulvestrant alone in subjects with advanced ER+/HER2- BrCa, as measured by ORR and CBR evaluated according to RECIST v. 1.1. ORR is defined as the proportion of subjects with response (CR or PR). CBR is defined as proportion of subjects with CR, PR, or SD that lasts for ≥ 24 weeks
- To evaluate the safety and tolerability of GS-5829 in combination with fulvestrant compared to fulvestrant alone in subjects with advanced ER+/HER2- BrCa
- To evaluate OS for subjects with advanced ER+/HER2- BrCa who received GS-5829 in combination with fulvestrant compared to fulvestrant alone

Exploratory objectives:

PRD

PRD

PRD

8.1.2. Primary Endpoints

Phase 1b Dose Escalation:

- Safety profile and tolerability of the combination of GS-5829 and fulvestrant as assessed by DLTs through Day 28 at each dose level of GS-5829

Randomized Phase 2 Dose Expansion:

- PFS defined as the interval from date of randomization to the earlier of the first documented confirmed disease progression or death from any cause

8.1.3. Secondary Endpoints

Phase 1b Dose Escalation:

- GS-5829 pharmacokinetic parameters (e.g., C_{max} , AUC_{tau})

Randomized Phase 2 Dose Expansion:

- Overall safety profile will be characterized by the type, frequency, severity, timing of onset, duration, and relationship to study treatment of any AEs or abnormalities in laboratory tests or ECGs
- ORR, defined as the proportion of subjects who achieve CR or PR, based on RECIST v. 1.1
- CBR, defined as the proportion of subjects who achieve CR, PR or SD that lasts for ≥ 24 weeks based on RECIST v. 1.1
- OS, defined as interval from date of randomization to date of death from any cause

8.2. Analysis Conventions

8.2.1. Analysis Sets

8.2.1.1. Intent-to-Treat (ITT) Analysis Set

The ITT analysis set includes all subjects who are randomized in the Randomized Phase 2 Dose Expansion phase of the study regardless of whether subjects receive any study drug(s), or receive a different regimen from the regimen they were randomized to. Treatment assignment will be designated according to randomization.

The analysis of PFS based on the ITT analysis set will be considered the primary analysis of the study. PFS will also be analyzed for each of the 2 strata separately.

This analysis set will be used in the analyses of PFS, ORR, CBR and OS. Subjects in the ITT analysis set who do not have sufficient baseline or on-study tumor status information to be adequately assessed for response status will be included in the denominators in the calculation of ORR and CBR.

8.2.1.2. The Per-Protocol (PP) analysis set

The PP analysis set includes data from subjects in the ITT analysis set who meet the general criteria defining the target population for this study: those who are adherent to the protocol, are compliant with study drug treatment, and are evaluable for relevant efficacy endpoints. Treatment assignment will be designated according to the actual treatment received. The PP analysis set will be used in sensitivity analyses of efficacy endpoints.

8.2.1.3. Safety Analysis Set

The Safety Analysis Set includes subjects who receive ≥ 1 dose of study drug. This analysis set will be used for the analyses of safety endpoints, study treatment administration and study drug compliance.

8.2.1.4. DLT-Evaluable Analysis Set

The DLT-Evaluable Analysis Set includes all Phase 1b Dose Escalation subjects in the Safety Analysis Set who complete all treatment and safety procedures through Day 28, or experienced a DLT prior to Day 28. Subjects who are not evaluable for DLT determination may be replaced.

8.2.1.5. Pharmacokinetics and Pharmacodynamics Analysis Sets

The pharmacokinetics and pharmacodynamics Analysis Sets will consist of all subjects in the Safety Analysis Set who have the necessary baseline and on-study measurements to provide interpretable results for the specific parameters of interest.

8.2.1.6. Biomarker Analysis Set

The Biomarker Analysis Sets include data from subjects in the Safety analysis set who have the necessary baseline and on-study measurements to provide interpretable results for the specific parameters of interest.

8.3. Data Handling Conventions

Subject listings will be created for important variables from each eCRF module. Summary tables for continuous variables will contain the following statistics: N (number in population), n (number with data), mean, standard deviation (StD), 95% confidence intervals (CIs) on the mean, median, the first and third quartiles, minimum, and maximum. Summary tables for categorical variables will include: N, n, percentage, and 95% CIs on the percentage. Unless otherwise indicated, 95% CIs for binary variables will be calculated using the binomial distribution (exact method) and will be 2-sided. Data will be described and summarized by relevant dose level (Phase 1b Dose Escalation), time point and treatment group for the corresponding analysis sets. As appropriate, changes from baseline to each subsequent time point will be described and summarized by dose level and treatment group. Similarly, as appropriate, the best change from baseline during the study will also be described and summarized by dose level and treatment group. Graphical techniques (e.g., waterfall plots, Kaplan-Meier curves, line plots) may be used when such methods are appropriate and informative.

The baseline value will be the last (most recent) pre-treatment value. Data from all sites will be pooled for all analyses. Analyses will be based upon the observed data unless methods for handling missing data are specified. If there is a significant degree of non-normality, analyses may be performed on log-transformed data or nonparametric tests may be applied, as appropriate.

8.4. Demographic Data and Baseline Characteristics

Subject demographic and baseline characteristics will be listed and summarized by dose level (Phase 1b Dose Escalation) and by treatment group for the Safety Analysis Set.

8.5. Efficacy Analysis

8.5.1. Primary Analysis

The difference in PFS between the treatment arms will be assessed in the ITT analysis set using the log-rank test. Kaplan-Meier estimates and plots, hazard ratios and corresponding 95% CIs will be presented.

Subjects who withdraw from the study or are lost to follow-up without disease progression or death will be censored on the date of the last visit when lack of disease progression was documented. Subjects who have progression or die after ≥ 2 consecutive missing tumor assessments will be censored at the last time prior to the missing assessments that lack of

definitive progression was objectively documented. Subjects without any adequate post-baseline disease assessment will be censored on the date of first study dose.

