A Safety Analysis Set for this study consists of all subjects who receive ≥ 1 dose of study drug. Other analysis sets (DLT evaluable analysis set, pharmacokinetics analysis set, and biomarker analysis set) will be used for the corresponding analyses.

Subject characteristics and study results will be described and summarized by dose level, treatment arm and study visit for the relevant analysis sets. Descriptive summaries will be prepared to show sample size, mean, standard deviation (StD), 95% confidence intervals (CIs) on the mean, median, minimum and maximum for continuous variables, and counts, percentages and 95% CIs on the percentage for categorical variables.

Kaplan-Meier estimates and plots will be provided for PFS and OS. The log-rank test will be used to compare PFS and OS between subjects who received GS-5829 + fulvestrant and those who received fulvestrant alone. ORR and CBR will be calculated along with the 95% CIs based on exact method and compared between treatment arms by Fisher's exact test. Based on the Safety Analysis Set, information regarding study drug administration, study drug compliance and safety variables will be described and summarized.

Using data from the relevant Analysis Sets, GS-5829 plasma concentrations will be summarized. Pharmacodynamic markers will also be described and summarized. Plasma concentrations of GS-5829 metabolite(s), fulvestrant and exemestane may also be determined.

Sample Size

Up to approximately 30 subjects will be enrolled in the Phase 1b Dose Escalation portion of the study.

Total enrollment will be approximately 120 subjects in Randomized Phase 2 Dose Expansion portion. Approximately 80 subjects will be randomized to receive GS-5829 in combination with fulvestrant and 40 subjects will receive fulvestrant alone in a 2:1 ratio. One hundred twenty subjects will provide 88 events in total and greater than 90% power to detect the difference in PFS between the two treatment arms with 0.1 one-sided significance level, assuming a median PFS of 4 months for subjects who receive fulvestrant alone, a median PFS of 8 months in subjects who receive GS-5829 in combination with fulvestrant, accrual period of 9 months and total study duration of 19 months and a drop-out rate of 10% by 12 months. Within each stratum of naïve or progressed prior CDK4/6 inhibitor subjects, the power will be 80% with target number of 60 subjects (44 events).

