For certain toxicities, such as laboratory assessments without a clear clinical correlate, a discussion between the investigator and the Gilead medical monitor may take place to determine if this AE should be assessed as a DLT. However, any Grade 3 or Grade 4 elevation in aspartate transaminase (AST) or alanine transaminase (ALT) associated with a Grade 2 elevation in bilirubin that is at least possibly related to study drug will be considered a DLT.

Randomized Phase 2 Dose Expansion:

Approximately 120 female subjects who are post-menopausal with ER+/HER2- BrCa and who have had disease progression following endocrine therapy will be randomized in a 2:1 ratio to receive fulvestrant + GS-5829 or fulvestrant alone. Randomization will be stratified by prior cyclin-dependent kinase 4/6 (CDK4/6) inhibitor plus AI status (naïve vs. progressed). The target number of subjects in each of the 2 strata will be approximately 60 (40 for GS-5829 in combination with fulvestrant and 20 for fulvestrant alone). GS-5829 and fulvestrant will be initiated on C1D1. Each cycle consists of 28 days.

Figure 3-1. Randomized Phase 2 Dose Expansion

* Randomization will be stratified by prior CDK4/6 inhibitor plus AI status (naïve vs. progressed). The target number of subjects in each of the 2 strata will be approximately 60 (40 for GS-5829 in combination with fulvestrant and 20 for fulvestrant alone).

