8.5.2. Secondary Analyses

The best overall response will be summarized by each response category as CR, PR, SD and PD by treatment arms. Fisher's exact test will be used to compare ORR and CBR between treatment arms. The 2-sided 95% CIs for ORR and CBR will be calculated based on exact method. The difference in OS between the treatment arms will be assessed using the log-rank test. Kaplan-Meier estimates and plots, hazard ratios and corresponding 95% CIs will be presented.

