8.9. Sample Size

The sample size of the Phase 1b Dose Escalation portion of the study will be determined based on the number of dose levels evaluated and the emerging drug-related toxicities, and may enroll up to approximately 30 subjects.

Approximately 120 subjects will be enrolled in the Randomized Phase 2 Dose Expansion portion of this study. Approximately 80 subjects will be randomized to receive GS-5829 in combination with fulvestrant and 40 subjects to receive fulvestrant alone in a 2:1 ratio. The sample size of 120 subjects will provide 88 events in total and greater than 90% power to detect the difference in PFS between the two treatment arms with 0.1 one-sided significance level, assuming a median PFS of 4 months for subjects who receive fulvestrant alone, a median PFS of 8 months in subjects who receive GS-5829 in combination with fulvestrant, accrual period of 9 months and total study duration of 19 months and a drop-out rate of 10% by 12 months. Within each stratum of naïve or progressed prior CDK4/6 inhibitor plus AI subjects, the power will be 80% with target number of 60 subjects (44 events).

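### The primary PFS log-rank test and hazard ratio, and the OS test, do not carry the factor by which Phase 2 randomization is stratified

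*Protocol*

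**What the plan says.** Protocol 3.2 (Study Design) states: "Randomization will be stratified by prior cyclin-dependent kinase 4/6 (CDK4/6) inhibitor plus AI status", with the levels naïve and progressed. The target is about 60 subjects per stratum, 40 on the combination and 20 on fulvestrant alone. The synopsis and 5.1 repeat this.

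For the primary analysis, 8.5.1 states: "The difference in PFS between the treatment arms will be assessed in the ITT analysis set using the log-rank test". It adds Kaplan-Meier estimates and hazard ratios with 95% CIs. The synopsis, under Statistical Methods, states: "The log-rank test will be used to compare PFS and OS between subjects who received GS-5829 + fulvestrant and those who received fulvestrant alone". Section 8.5.2 gives a log-rank test and hazard ratio for OS in the same terms. For the response endpoints, Fisher's "exact test will be used to compare ORR and CBR between treatment arms".

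None of these passages calls a test or hazard ratio stratified or adjusted. The strata enter the analysis in one place, 8.2.1.1: "PFS will also be analyzed for each of the 2 strata separately".

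Section 8.9 sizes the trial "with 0.1 one-sided significance level", with one pair of medians (4 and 8 months). It claims more than 90% power overall with 88 events, and 80% in either stratum with 44.

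**The concern.** A factor used to stratify randomization is normally carried into the primary test. This protocol treats the factor as important: each stratum has its own enrolment target, its own PFS analysis and its own power statement.

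If the strata differ in prognosis, leaving the factor out has two effects.

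- **Conservative test.** Stratified randomization balances the arms within strata, but the pooled log-rank variance gives no credit for that balance.
- **Attenuated hazard ratio.** Patients in the poorer stratum fail earlier, and faster on control. Over time the control risk set holds relatively more patients from the better stratum, and the pooled hazard ratio drifts toward 1.

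At stake are some power and an understated effect estimate, which matters because a Phase 2 hazard ratio informs what is done next. False-positive control is not at stake.

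**Working it through.** **1. Reproduce the plan's figures.** Inputs from 8.9: medians 4 and 8 months (HR 0.5 if exponential), 2:1 allocation, one-sided 0.10 (z = 1.2816), 9 months' accrual, 19 months in total, drop-out 10% by 12 months.

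Schoenfeld power = Φ(√(d·p(1−p))·|ln HR| − z), with p = 2/3:
- d = 88: √(88 × 2/9) × 0.693 − 1.282 = 3.065 − 1.282 = 1.78, so power is 96.3% (stated: more than 90%).
- d = 44: 2.167 − 1.282 = 0.89, so power is 81.2% (stated: 80%).

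Expected events use event hazard λ = ln 2/median, drop-out hazard η = −ln(0.9)/12 and h = λ + η. The event probability is (λ/h)·[1 − (e^(−10h) − e^(−19h))/(9h)], which gives 0.876 on control and 0.673 on the combination. So 40 × 0.876 + 80 × 0.673 = 88.9 events.

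The plan's figures reproduce, and they do so with a plain log-rank calculation.

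**2. Compare the two tests.** Simulation: 60 per stratum, 2:1 within stratum, exponential PFS, accrual and drop-out as above, analysis at the 88th event, one-sided 0.10, 6,000 trials per setting. R is the hazard ratio between strata, with the geometric mean of the control medians held at 4 months. **R and the HR of 0.65 are assumptions; neither is in the documents.** Entries are unstratified / stratified, in %.

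| R | Power, HR 0.5 | Power, HR 0.65 | One-sided error |
|---|---|---|---|
| 1 | 96.4 / 96.2 | 74.1 / 73.6 | 10.9 / 10.7 |
| 1.5 | 96.2 / 96.6 | not run | 9.9 / 10.0 |
| 2 | 95.8 / 96.7 | 71.4 / 74.6 | 9.4 / 10.2 |
| 3 | 94.1 / 97.0 | 65.7 / 73.4 | 8.4 / 10.6 |
| 4 | 90.6 / 96.6 | not run | 7.0 / 10.6 |

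Monte Carlo error is about 0.2 to 0.4 points for power at HR 0.5 and for the error rates, and about 0.6 for power at HR 0.65. Further independent simulations gave the same picture. At 2-fold the loss at HR 0.65 was up to 3.6 points. At 3-fold it was about 3 points at HR 0.5 and about 8 at HR 0.65, with unstratified error between 8.0% and 8.8%.

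**3. Separate the size difference from the gain.** At R = 3 the unstratified test runs below 10% and the stratified test slightly above it, so raw power flatters stratification. With both tests set to exactly 10% size:
- Control medians 6 and 2 (3-fold), HR 0.5: 94.4% against 96.1%, a loss of 1.7 points. A second run gave 1.2.
- The same medians, HR 0.65: 69.9% against 73.5%, a loss of 3.6 points. A second run gave 2.5.
- Medians 5 and 3: 96.0% against 96.2%, and 72.1% against 72.2%, effectively nothing.

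**4. Estimate.** Median estimated hazard ratio, unstratified against stratified (1,500 trials):
- 2-fold, truth 0.50: 0.523 against 0.501.
- Medians 6 and 2, truth 0.50: 0.557 against 0.499.
- Medians 6 and 2, truth 0.65: 0.698 against 0.654.

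**The case against.** The strongest reply is that the plan delivers what it promises. The claim of more than 90% power never rested on a stratified test. Section 8.9 assumes the same medians in both strata, and on that assumption stratifying gains nothing. At HR 0.5, power stays above 90% even at a 4-fold stratum difference. The larger losses need both a strong prognostic factor and a weaker effect than the design's, and at 3-fold about half or more of the raw gap is a size difference. All of this stands. A reader might infer that the design discards power it had already paid for; the documents do not support that.

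It can also be said that the strata are not ignored, since PFS is analysed within each. That is true, but separate analyses do not bring the factor into the primary test or its hazard ratio.

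The word unstratified is inferred from silence. It is the plain reading; if a stratified test was intended, the primary analysis is under-specified and the same edit settles it.

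Two further inferences fail. SAP 3.3, which says no strata will be used, concerns the Phase 1b data and is no evidence about the Phase 2 test. And Fisher's exact test for ORR and CBR is valid as it stands; no calculation here shows a loss from it.

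**Conclusion.** The point holds as a mismatch between randomization and analysis, with a modest and conditional cost. With equal prognosis in the strata there is no loss. At a 2-fold hazard difference the loss is about 1 point of power at HR 0.5 and about 3.5 at HR 0.65. At 3-fold it is about 3 and 8 points, or about 1 to 2 and 2.5 to 4 at equal size, with unstratified one-sided error of about 8 to 9% against the nominal 10%. The hazard ratio is pulled toward 1 in step: 0.523 at 2-fold and 0.557 at 3-fold when the truth is 0.50.

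These sizes rest on exponential PFS, a common treatment effect in both strata, and assumed prognostic differences that the documents do not give. It would be too strong to say that the error rate will fall below 10%: that happens clearly only when the strata differ strongly.

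SAP section 1 (Introduction) records that the study stopped during dose escalation, and SAP section 3 plans no formal testing. No reported result is affected.

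**What to change.** In protocol 8.5.1, for OS in 8.5.2, and in the synopsis under Statistical Methods, specify a log-rank test stratified by prior CDK4/6 inhibitor plus AI status (naïve or progressed), with the hazard ratio from a Cox model stratified by the same factor. Keep the unstratified test and hazard ratio as sensitivity analyses. A stratified test for ORR and CBR is optional.

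The cost is a short edit in three places. Sample size, event target and data collection do not change, because the factor is already recorded for randomization. If the strata turn out alike, the stratified test gives up nothing material (96.2% against 96.4% at HR 0.5, within simulation error).

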6.2.10. Disease Assessments

6.2.10.1. CT or MRI

Subjects will be assessed by CT scan with contrast (or MRI, if unable to tolerate CT contrast) of the chest, abdomen and pelvis to document metastatic disease, identify target lesions and to assess response as per RECIST 1.1 (refer to [Appendix 7](#)). The same assessment methods should be used for the subject throughout all treatment cycles. CT, or MRI scans will be obtained at the applicable study visits per the Study Procedures Table ([Appendix 2](#)) and transferred to a central vendor for storage.

In subjects who cannot tolerate iodinated contrast, a CT of the lung without contrast and MRI of the abdomen and pelvis should be performed. Imaging by CT scan (with contrast) or MRI or applicable scan will be performed at Screening (within 28 days before C1D1 if the scan was performed as part of standard medical practice) and every 8 weeks for the first year and then every 12 weeks during the treatment period regardless of cycle number or dose interruption. During the treatment, scans may be performed at time points other than 12 weeks, as clinically indicated, to assess tumor progression.

Tumor burden will be characterized at baseline and subsequent response assessments will be carried out according to the RECIST v. 1.1 (refer to [Appendix 7](#)). The same radiographic procedure and specification (e.g., the same contrast agent, slice thickness, etc.) used to define measurable lesions at baseline must be used throughout the study for each subject.

Subjects who discontinue study treatment for reasons other than disease progression will continue to have tumor assessments performed during the follow up visits every 8 weeks for the first year and then every 12 weeks until disease progression, initiation of new anti-cancer therapy, or discontinuation from the overall study participation (death, subject's request, lost to follow-up) whichever happens first. Every effort should be made to perform a last tumor assessment before starting a new anti-cancer therapy. Additional unscheduled tumor assessments may be performed as clinically indicated at any time.

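### The Phase 2 PFS rule censors subjects with no adequate post-baseline assessment at first dose without exempting deaths; this conflicts with the endpoint definition and leaves some never-dosed ITT subjects with no date under that rule

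*Protocol*

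**What the plan says.** Protocol Section 8.1.2 gives the Phase 2 primary endpoint as "PFS defined as the interval from date of randomization to the earlier of the first documented confirmed disease progression or death from any cause". Section 8.2.1.1 places every randomized subject in the ITT set, "regardless of whether subjects receive any study drug(s), or receive a different regimen from the regimen they were randomized to". Section 8.5.1 names the primary test: "The difference in PFS between the treatment arms will be assessed in the ITT analysis set using the log-rank test".

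The second paragraph of Section 8.5.1 then has three censoring sentences:

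1. "Subjects who withdraw from the study or are lost to follow-up without disease progression or death will be censored" at the last visit that documented no progression.
2. Those who progress or die after two or more "consecutive missing tumor assessments will be censored at the last time prior to the missing assessments that lack of" progression was documented.
3. "Subjects without any adequate post-baseline disease assessment will be censored on the date of first study dose".

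Section 6.2.10.1 schedules imaging "every 8 weeks for the first year and then every 12 weeks during the treatment period", so the first planned post-baseline scan falls at week 8.

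SAP Section 6.1.1, written for the Phase 1b data, repeats the third rule with Study Day 1 as the date, again without an exception for death. SAP Section 1 records that the study stopped during dose escalation and that Phase 2 was not started.

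**The concern.** The first two sentences limit how they treat death. The first covers only subjects who have neither progressed nor died. The second censors a death only when at least two consecutive assessments were missed before it. The third has neither limit. A programmer who follows it literally would take a subject who died at week 5, an event by definition, and censor her at or near time zero.

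Deaths before the first assessment would then leave both the event count and the risk set. If they were more frequent when GS-5829 is added, for instance through toxicity, the primary analysis would not see them and the hazard ratio would move toward benefit.

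The date is a second defect. PFS runs from randomization, but the rule points to first dose, and the ITT set keeps subjects who have no first dose.

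**Working it through.** **The text.** Take a randomized subject who dies at week 5 with no post-baseline assessment.

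- Section 8.1.2: event on the date of death.
- Section 8.5.1, first sentence: does not apply, because she died.
- Second sentence: does not apply, because no scheduled assessment had been missed.
- Third sentence: applies, and censors her at first dose.

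The definition and the third sentence give different answers, and nothing says which prevails.

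Now take a randomized subject who is never dosed and has no post-baseline assessment. The third sentence gives no date. If she withdraws, the first sentence might supply a last-visit date, but precedence is again not stated.

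**The plan's own figures.** Inputs from Protocol Section 8.9: 80 and 40 subjects, medians 8 and 4 months (HR 0.50 if exponential), one-sided alpha 0.10, accrual 9 months, total duration 19 months, drop-out 10% by 12 months.

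- Expected events per arm = n × λ/(λ+η) × {1 − [exp(−10(λ+η)) − exp(−19(λ+η))] / [9(λ+η)]}, with λ = ln 2/median and η = −ln(0.9)/12. This gives 53.9 + 35.0 = 88.9, against 88 stated.
- Power = Φ(√(d × 2/3 × 1/3) × ln 2 − 1.2816). With d = 88, Φ(3.065 − 1.282) = 96.3%, consistent with the stated figure of more than 90%. With d = 44, 81.2% against 80% stated.

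The sample-size figures reproduce and are not in dispute.

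**Effect on power.** The documents give no early-death rate, so a range is assumed. Each row removes that share of the 120 subjects from the 88 events, and half as many from the 44 events of a stratum.

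| Early deaths, no assessment | Events removed | Overall power | Per-stratum power |
|---|---|---|---|
| 1% | 1.2 | 96.1% | 80.8% |
| 2% | 2.4 | 95.9% | 80.4% |
| 5% | 6 | 95.3% | 79.1% |
| 10% | 12 | 94.1% | 76.8% |

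**Effect on the hazard ratio.** Trials were simulated with 80 and 40 subjects, exponential PFS detected at scheduled scans, the protocol's accrual and drop-out, and early deaths spread uniformly before week 8. Each was analysed by Cox regression twice: early deaths counted, then censored at time zero. The table uses Efron ties.

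| Early deaths, GS-5829 arm vs control | HR otherwise | Deaths counted | Deaths censored |
|---|---|---|---|
| 5% vs 5% | 0.5 | 0.52 | 0.49 to 0.50 |
| 10% vs 2.5% | 0.5 | 0.59 | 0.50 |
| 10% vs 2.5% | 1.0 | 1.09 to 1.10 | 0.99 to 1.01 |

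Ranges are from repeat runs. Breslow ties shift the first two rows (0.56 to 0.54 and 0.64 to 0.54) but give nearly the same differences. At 2% vs 1% the shift is about 0.02; at equal rates of 1% to 2% it is 0.01 or less.

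**Effect on the decision.** The table gives the share of 10,000 simulated trials per setting, with event times in continuous time, that reach one-sided 0.10 on the log-rank test.

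| Early deaths, GS-5829 arm vs control | Medians otherwise (months) | Deaths counted | Deaths censored |
|---|---|---|---|
| 5% vs 5% | 8 vs 4 | 96.0% | 96.5% |
| 10% vs 0% | 8 vs 4 | 87.8% | 96.6% |
| 10% vs 0% | 4 vs 4 | 4.0% | 10.7% |
| 5% vs 0% | 4 vs 4 | 6.9% | 10.6% |

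**The case against.** The strongest reply is that the third sentence was meant only for subjects without an event. The endpoint definition points that way, and so does the second sentence, which would be odd if all earlier deaths without an assessment were already censored. The SAP gives some support. Where Section 6.1.1 intends to override death, for subjects with no baseline assessment, it says so expressly; its rule for no post-baseline assessment has no such words. This stands as evidence of intent, so a reader should not infer that the plan deliberately discards early deaths. It does not settle the text: the sentence is unqualified and both documents carry it without an exception.

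Four further limits stand.

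- The rule turns on an adequate disease assessment, not a scheduled scan. Unscheduled assessments are allowed at any time, and CT or MRI is due at end of treatment if none was done in the previous 4 weeks. Some patients who deteriorate early would therefore escape the rule. The simulations treat every death before week 8 as unassessed, so they are upper bounds for a given early-death rate.
- Eligibility requires life expectancy of at least 3 months and ECOG status of at most 1, and SAP Section 7.1.6.2 reports no deaths in the study. Both point to low early-death rates.
- A reader might infer that all never-dosed ITT subjects lack a censoring date. The gap reaches only those who also have no post-baseline assessment, and the first sentence may cover some of them.
- A reader might infer inflated type I error. The simulations do not show that: with equal hazards and no early deaths the test rejects in 10.3% of trials, against 10.7% with a 10% excess of early deaths censored. The test fails to register the harm; it does not exceed its nominal level in any material way.

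Deaths would also still appear in the OS analysis and the adverse-event tables.

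**Conclusion.** The point holds as a defect in the wording of the planned Phase 2 primary analysis. Followed literally, the third sentence of the censoring paragraph in Section 8.5.1 contradicts the PFS definition for deaths before any adequate post-baseline assessment, and it supplies no date for never-dosed ITT subjects who lack such an assessment.

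The size depends on assumed early-death rates. It is small when these deaths are rare or balanced: an HR shift of about 0.02 to 0.03 or less, and overall power still 94.1% with 10% early deaths. It is material only if they are clearly more common with GS-5829: 0.59 to 0.50 at 10% vs 2.5%, as an upper bound. The direction is then toward benefit.

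The documents do not support saying that any result was biased. Phase 2 did not open, the SAP plans no formal testing, its efficacy set contains only dosed subjects, and no death was reported.

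**What to change.** Replace the third sentence with two, and state that they take precedence over the other two sentences for subjects with no adequate post-baseline assessment:

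- A death from any cause before any adequate post-baseline disease assessment is a PFS event on the date of death if fewer than two scheduled assessments were missed.
- All other subjects with no adequate post-baseline assessment, whether alive, never dosed, or dead after two or more missed scheduled assessments, are censored on the date of randomization.

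The last category needs naming. Without it, those deaths fall back to the missed-assessment rule, where the last documented lack of progression could be no later than the baseline scan, before PFS time begins.

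The cost is two sentences of protocol or SAP text. No new data are needed: survival is already followed for OS (Protocol Section 6.7), and randomization dates exist for every ITT subject.
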